A Randomized, Controlled Trial to Evaluate the Role of Oral Azithromycin in the Treatment of Symptomatic Meibomian Gland Disease and its effect on the Ocular Surface Microbiome

NCT Number NCT03953118

Date: January 2, 2018

Principal Investigator: [name]
Co-Investigator: [name] PhD

i. Background and Significance

Dry eye syndrome (DES) is a persistent feeling of ocular discomfort that encompasses dryness, irritation, foreign body sensation and burning. In the United States, it is the most common non-refractive cause of visits to eye care providers¹, and has been shown to have a significant impact on quality of life of patients who suffer from this condition². It is not one disease state, but rather is composed of multiple different entities whose end stage results in the symptoms encompassed by DES. The most common cause of DES is Meibomian gland disease (MGD).³

The Meibomian glands are modified sebaceous glands that line the upper and lower eyelids and have orifices opening onto the eyelid margin.⁴ The secretory product of the Meibomian glands is a finely tuned mixture of lipids with high spreadability and low surface tension that coat the ocular surface and provide an evaporative barrier against aqueous tear loss.⁵ A change in the composition of the lipids can cause the tear film to become unstable, either breaking up prematurely or failing to spread properly after blinking, which leaves the underlying corneal epithelium exposed.⁶

Numerous treatments for MGD have been proposed, ranging from heating the glands⁷ to topical anti-inflammatories^{8, 9}, oral omega-3 fatty acids^{10, 11}, and topical¹² or oral^{13, 14} antibiotics. The role of topical anti-inflammatories as effective has been well-established, but the role of antibiotics is less clearly defined. Some clinicians advocate using antibiotics to reduce the burden of bacteria on the ocular surface¹⁵, but the utility of this has never been established¹⁶, nor have there been any causal relationship demonstrated between a bacterial pathogen and MGD¹⁷.

A competing theory for the use of antibiotics to treat MGD is that they exhibit an anti-inflammatory effect on the Meibomian glands, thereby improving the composition of secreted lipid. The macrolide and tetracycline antibiotics have been shown to have a anti-inflammatory effects in addition to their antimicrobial action.¹⁸ Azithromycin has also been shown to affect the lipid composition of cultured human Meibomian gland cells.^{19, 20}

The use of antibiotics in the treatment of MGD is an important question to address, as MGD is both an extremely common and chronic disease, and patients are often treated repeatedly. It has been well established that the use of topical and oral antibiotics can induce resistance in bacteria, and thus use of antibiotics should be limited only to cases where there is a definite treatment benefit. Given the widespread use of antibiotics in treatment of MGD, one would hope that there is solid evidence as to the benefit of oral antibiotics as compared to placebo, however evidence based on well-designed clinical trials is sorely lacking.¹⁶

The pathogenicity of bacteria in MGD has never been demonstrated.¹⁷ It may be because MGD is a non-infectious disease, or it may be because the organism is difficult to identify using standard culture techniques. With the dawn of 16s ribosomal DNA amplification techniques, it has become apparent that the microbiological inhabitants of the ocular surface are far more diverse and numerous than what has been identified using standard culture techniques. Although studies on the ocular microbiome are still in their infancy, differences in microbiological populations have been identified in patients with DES and in contact lens wearers. The microbiome in patients with MGD and in patients who have been treated for MGD remains

unstudied using modern DNA-based techniques and is a ripe area for research, which this project proposes to address.

ii. Preliminary Studies

There have been two published studies looking at oral azithromycin in the treatment of MGD. Oral azithromycin dosed at 1 gram per week for 3 weeks, has been previously studied in a retrospective case series conducted at the F.I. Proctor Foundation at UCSF. In this study, seventy-five percent of subjects reported symptomatic improvement in ocular surface discomfort at a mean follow up time of 5.6 weeks.¹³ This was a retrospective analysis, and subjects were on multiple different medications during the study period, which may have affected the outcome. Oral azithromycin has also been studied at a dose of 500mg/day for 3 days, repeated every 7 days for 3 cycles, in a prospective, open-label trial of 13 patients. In this study, the authors reported improvement in both the symptoms and signs of MGD at an undefined end point.²¹

9. Limbal stem cell deficiency
10. Oral or topical ophthalmic antibiotic use within the last 90 days
11. Oral prednisone use >5 mg per day
12. Topical ophthalmic steroid use within the past 30 days
13. Topical ophthalmic anti-inflammatory (including non-steroidal anti-inflammatories, lifitegrast, or cyclosporine) use within the past 30 days

Table 1: Medications that Prolong QT Interval

Medication	Use	Medication	Use
Amiodarone	Antiarrhythmic	Flecainide	Antiarrhythmic
Amisulphride	Antipsychotic	Haloperidol	Antipsychotic
Amitryptyline	Antidepressant	Hydroxychloroquine	Anti-Malarial
Astemizole	Antihistamine	Imipramine	Antidepressant
Chloroquine	Anti-Malarial	Loratadine	Antihistamine
Chlorpromazine	Antipsychotic	Nortriptyline	Antidepressant
Clarithromycin	Antibiotic	Olanzapine	Antipsychotic
Desipramine	Antidepressant	Procainamide	Antiarrhythmic
Diphenhydramine	Antihistamine	Quetiapine	Antipsychotic
Disopyramide	Antiarrhythmic	Quinidine	Antiarrhythmic
Doxepin	Antidepressant	Quinine	Anti-Malarial
Droperidol	Antipsychotic	Sotalol	Antiarrhythmic
Encainide	Antiarrhythmic	Terfanadine	Antihistamine
Erythromycin	Antibiotic	Thioridazine	Antipsychotic

VII. Main Outcome Measure

The primary outcome will be change in OSDI score from enrollment to 1 month.

Secondary Outcome Measures

1. Difference in alpha diversity of ocular surface microbiome as assessed by Shannon's diversity index between azithromycin and placebo groups at 1 and 3 months.
2. Change in alpha diversity of ocular surface microbiome as assessed by Shannon's diversity index between azithromycin and placebo groups between 0 and 1 month.
3. Change in OSDI score from enrollment to 3 months
4. Change in Neuropathic Pain Score Inventory for the Eye (NPSI-E) from enrollment to 1 and 3 months
5. Change in 5-Item Dry Eye Questionnaire (DEQ-5) from enrollment to 1 and 3 months
6. Change in meibomian gland grading from enrollment to 1 and 3 months
7. Change in SICCA score from enrollment to 1 and 3 months
8. Change in OSI (Ocular Surface Index) score at 1 and 3 months

VIII. Statistical Analysis

For continuous outcomes, a two-tailed t test for significance will be used.

For microbiome outcomes, the alpha diversity (local species pool) of the population will be analyzed and compared pre-and post-treatment within and between the azithromycin and control groups. The difference between the bacterial microbiome in the azithromycin and placebo arm will be assessed using a PERMANOVA with an L^2 norm distance measure. Secondary analyses will include L^1 and L^0 norms, as well as a phylogenetic distance. In addition, we will assess whether bacterial alpha diversity is decreased in the antibiotic treated arm with the primary outcome being the Simpson's index (L^2), with secondary analyses assessing Shannon's (L^1) and Richness (L^0).

IX. Study Sizing

The number of patients was calculated by assuming a 20% difference in Ocular Surface Disease Index (OSDI)²⁴ score at the primary outcome between treatment and placebo groups, with 80% power and a significance level of 0.05. This yielded a total of 16 patients per arm. To account for loss to follow up, a total of 19 patients per arm will be recruited.

X. Placebo

The oral azithromycin placebo will be a sugar pill, and will be made by the UCSF Investigational Pharmacy.

XI. Non-Medication Intervention

All patients will receive education regarding non-medication interventions for their Meibomian gland disease. This will be instruction to perform warm compresses over both eyes for 10 minutes twice per day. The handout that will be given to patients is available in the Manual of Procedures (MOP).

XII. Masking

The UCSF Investigational pharmacy will perform randomization according to randomization schedule. All masking of investigational medications will be performed by the UCSF Investigational Pharmacy.

Azithromycin tablets will be over-encapsulated for masking purposes to match the placebo pills. Artificial tears will be used as the placebo for dexamethasone, and both will be in identical eye dropper vials.

Both patients and physicians will be masked as to study assignment. The clinical coordinator and the Investigational Pharmacy will have access to the randomization key.

XIII. Schedule of Procedures

The initial visit will be at enrollment. The 1 month visit will be 21-35 days after the initial visit, and the 3 month visit will be 76-96 days after the initial visit.

Procedure	Initial	1 Month	3 Months
Visual Acuity	X	X	X
Refraction	X		
IOP	X	X	X
Schirmer's	X	X	X
TBUT	X	X	X
MGE	X	X	X
SICCA Score	X	X	X
NSPI-E	X	X	X
DEQ-5	X	X	X
OSDI	X	X	X
PHQ-9	X		

XIV. Patient-Reported Instruments

1. NPSI-E – Neuropathic pain inventory
 - i. Number of Questions – 12
 - ii. Time to Complete -
2. DEQ-5 – Dry eye questionnaire 5
 - i. Number of Questions –
 - ii. Time to Complete –
3. OSDI – Ocular surface disease index
 - i. Number of Questions – 12
 - ii. Time to Complete - 5 minutes

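### Section VII tests the 1-month Shannon diversity effect twice with no rule on which result decides, and its 3-month comparison has no month-0 term; one baseline-adjusted test per visit would be clearer and usually more powerful

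*Combined protocol and SAP*

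**What the plan says.** The Secondary Outcome Measures list in section VII opens with two Shannon diversity items:

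- Item 1 is the difference in Shannon's index "between azithromycin and placebo groups at 1 and 3 months".
- Item 2: "Change in alpha diversity of ocular surface microbiome as assessed by Shannon's diversity index between azithromycin and placebo groups between 0 and 1 month".

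Section VIII names one test: "For continuous outcomes, a two-tailed t test for significance will be used". It adds that alpha diversity "will be analyzed and compared pre-and post-treatment within and between the azithromycin and control groups", but names no visit, model or covariate for that comparison. It also makes Simpson's index the leading alpha-diversity measure and places Shannon's index and richness in secondary analyses, whereas VII names only Shannon's. No baseline-adjusted model appears anywhere, and no sentence ranks item 1 against item 2.

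**The concern.** Allocation is randomised 1:1 (section iii), so the expected month-0 difference between arms is zero. The follow-up contrast in item 1 and the change contrast in item 2 therefore have the same expected value at 1 month. They are two estimates of one effect, not answers to two questions.

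Three things follow. The trial has two chances to declare a 1-month effect on Shannon diversity. When an effect is real, the two tests can give opposite verdicts, and the plan does not say which to believe. And neither test makes the best use of the month-0 value: item 1 ignores it, and item 2 subtracts it in full however well or poorly it predicts follow-up. At 3 months the only comparison listed in VII is the one that ignores it.

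This matters because the effect on the ocular surface microbiome is in the trial's title and these are the first two secondary outcomes. The OSDI primary outcome is not affected.

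**Working it through.** **Inputs.** From the documents: 16 evaluable patients per arm (19 recruited) and a 0.05 significance level, both from section IX, where they are set for OSDI; 1:1 allocation from section iii. The documents give no power figure for diversity, so there is no planned figure to reproduce. Assumed: equal variances at each visit, normal values, month-0 to follow-up correlation ρ of 0.3, 0.5 or 0.7 (with 0 as a limit), and a true difference of 1.024 SD. That difference is what an unpaired t test with 16 per arm (30 df) detects with 80% power.

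**Step 1: precision.** With SD = 1, the variance of each contrast is 2/16 times:

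- follow-up only: 1
- change: 2(1 − ρ)
- adjusted for month 0: 1 − ρ², times about 1 + 1/28 for estimating the slope (29 df)

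For follow-up only the noncentrality is 1.024/√(2/16) = 2.90. For change it is 2.90/√(2(1 − ρ)) = 2.45, 2.90 and 3.74 at ρ = 0.3, 0.5 and 0.7. For the adjusted test it is 2.98, 3.29 and 3.99.

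**Step 2: power at 1.024 SD** (noncentral t; simulation agrees).

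| ρ | Follow-up only | Change | Adjusted | Gain over better listed test | Gain over follow-up only |
|---|---|---|---|---|---|
| 0 | 80% | 51% | 78–79% | −1 to −2 | −1 to −2 |
| 0.3 | 80% | 66% | 82% | about 2 | about 2 |
| 0.5 | 80% | 80% | 89% | about 9 | about 9 |
| 0.7 | 80% | 95% | 97% | about 2 | about 17 |

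The fifth column is the relevant gain at 1 month, where both tests are listed. The last column is the relevant gain at 3 months, where only the follow-up comparison is listed; ρ is then the month-0 to month-3 correlation, a separate unknown.

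**Step 3: two tests of one effect.** The correlation between the two 1-month estimates is √((1 − ρ)/2) = 0.59, 0.50 and 0.39 at ρ = 0.3, 0.5 and 0.7, low enough for them to part company often. From 100,000 simulated trials per setting:

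| ρ | No effect: at least one significant | 1.024 SD: opposite verdicts |
|---|---|---|
| 0.3 | 8.8% | 27% |
| 0.5 | 9.2% | 23% |
| 0.7 | 9.3% | 20% |

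Each test alone, and the adjusted test, holds 5%.

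**Step 4: chance imbalance.** The standard error of the month-0 mean difference is √(2/16) = 0.35 SD. Given an observed month-0 difference D, the follow-up contrast is shifted by ρD and the change contrast by −(1 − ρ)D. For D = 0.35 SD the shifts are 0.11 and −0.25 SD at ρ = 0.3, 0.18 and −0.18 at ρ = 0.5, and 0.25 and −0.11 at ρ = 0.7. Because the signs are opposite, imbalance pushes the two listed tests apart. Adjustment removes the shift, up to error in the estimated slope.

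**The case against.** The strongest reply is that nothing here is an error. Both unadjusted comparisons are valid under randomisation, and each keeps its 5% level. These are secondary outcomes with no power claim. The list has six further items (3 to 8), most at two visits and without multiplicity control, so merging one pair changes the overall false-positive risk little. In VIII the between-arm microbiome difference is tested first by PERMANOVA, and Shannon's index ranks below Simpson's. The case for adjustment would apply equally to the OSDI change score and the other change outcomes. All of that stands, and it keeps this point at the level of an inexpensive improvement. It does not answer the narrower complaint that one effect at one visit has two tests and no stated decider.

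Three stronger readings are tempting, and the documents do not support them.

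- A reader might infer that the 3-month analysis never uses month 0. That is true only of the list in VII. The pre/post sentence in VIII is not limited to 1 month; the fair criticism is that it specifies no such test.
- A reader might infer that month-0 imbalance passes in full into item 1. It enters multiplied by ρ, and below ρ = 0.5 item 2 is the more affected.
- A reader might apply the 17-point gain to the 1-month analysis. There, the gain over the better listed test at ρ = 0.7 is only about 2 points.

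**Conclusion.** The point holds as a recommended improvement rather than a correction of an invalid analysis. The duplication and the missing decision rule follow from the text alone. Their size depends on 16 completers per arm, equal variances and normality. The either-test error of about 9% varies little across the correlations shown; the disagreement rate of 20% to 27% also depends on the assumed 1.02 SD effect.

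Any claim of lost power is conditional, because the documents give neither ρ nor an effect size for diversity. No unconditional statement that power is lost is supported: at ρ near zero, adjustment costs 1 to 2 points. What favours adjustment is that it does not require guessing ρ. At low ρ the change test is the weak one; at high ρ the follow-up test is; the adjusted test is within 1 to 2 points of the better one or ahead of it at every value examined.

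**What to change.** In VII, replace items 1 and 2 with one outcome: the between-arm difference in Shannon's index at 1 month and at 3 months, each from a linear model on arm and month-0 Shannon's index. In VIII, name this as the single between-arm test for that index at each time point, and report raw follow-up and change values as descriptive. Use the same model for Simpson's index and richness, and make VII and VIII agree on which index leads; otherwise the ambiguity only moves from two tests to three indices.

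The cost is wording, one degree of freedom, 1 to 2 points of power if month-0 diversity predicts nothing, and a simple pre-stated rule for patients without a usable month-0 sample. No additional sample is needed, since item 2 already requires month 0 and item 1 requires both follow-up visits. The schedule in XIII has no microbiome sampling row at any visit, however, so the sampling on which the adjusted analysis depends should be written there explicitly.

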4. PHQ-9 –
 - i. Number of Questions – 9
 - ii. Time to Complete – 5 min

XV.Ocular Surface Evaluation Procedures

The evaluation procedures should be performed in the order specified below to minimize disruption of the ocular surface.

1. Tear Breakup Time

Two people are required to measure tear breakup time, one who does the examination and one who holds timer. The tear breakup time should be measured prior to instillation of any anesthetic drops. A dry fluorescein strip should be touched lightly to the tear meniscus, and the patient instructed to blink several times. After even distribution of the fluorescein, the patient should be asked to blink again and then hold the eye open. The instant the patient holds their eye open an assistant should start a stopwatch. The examiner will remain looking at the ocular surface with the cobalt blue light at the slit lamp, and signal to the timer when the first break in the tear film occurs. This should be repeated a total of three times, and all three times recorded.

2. Meibomian Gland Grading

Meibomian glands will be evaluated using the handheld Meibomian gland expression device (MGED)²⁵ using the procedure described in Meadows, et al.²⁶

Two areas of the lower lid will be used for Meibomian gland grading – the temporal lower lid from the 4th-9th observable Meibomian gland orifice (counting from the lateral canthus) and the central lower lid from the 15th- 20th Meibomian gland orifice (counting from the lateral canthus).

The first step is observation of the glands, with assignment of a morphology score (Table 2). Following this, the glands will be expressed using the MGED, and meibum quality score will be assigned (Table 2).

Lid Morphology	Assigned Grade	Meibum Quality
No plugged glands	0	Clear, fluid meibum
Mild (1-2 glands plugged)	1	Granular or yellowish meibum
Moderate (3-4 glands plugged)	2	Whitish, semi-solid meibum
Severe (5+ glands plugged)	3	Solid, toothpaste-like meibum
-	4	No expressible meibum

Table 2: Meibomian gland scoring system, adapted from Meadows, et al²⁶

3. Schirmer Testing

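### The lead alpha-diversity index is not uniquely prespecified: Section VII lists only Shannon's index, while Section VIII makes Simpson's the lead and Shannon's secondary.

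*Combined protocol and SAP*

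**What the plan says.** Section VII lists eight secondary outcomes, and the first two concern alpha diversity. Item 1 is "Difference in alpha diversity of ocular surface microbiome as assessed by Shannon's diversity index between azithromycin and placebo groups at 1 and 3 months". Item 2 is "Change in alpha diversity of ocular surface microbiome as assessed by Shannon's diversity index between azithromycin and placebo groups between 0 and 1 month". Neither Simpson's index nor richness appears anywhere in Section VII.

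Section VIII opens with a general rule: "For continuous outcomes, a two-tailed t test for significance will be used". It then says that alpha diversity "will be analyzed and compared pre-and post-treatment within and between the azithromycin and control groups", without naming an index. Community composition "will be assessed using a PERMANOVA with an L^2 norm distance measure". A further sentence asks whether alpha diversity falls in the antibiotic arm, "with the primary outcome being the Simpson's index (L^2), with secondary analyses assessing Shannon's (L^1) and Richness (L^0"). That sentence gives no visit.

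**The concern.** The index that defines the listed outcomes is demoted in the analysis section, and the index that leads in the analysis section is not a listed outcome. A reader cannot tell which result is the prespecified test of alpha diversity.

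The choice can matter. Simpson's index is driven by the dominant taxa, while Shannon's gives rarer taxa more weight, so the two can point in different directions on the same data. While two sections name different leads, whichever gives the more favourable result can be reported as the planned one, with a section of the protocol to cite for it. The effect on the ocular surface microbiome is in the trial's title, so this result will be read closely even though it is secondary.

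**Working it through.** **1. The two sections side by side.**

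| | Section VII, items 1 and 2 | Section VIII |
|---|---|---|
| Lead index | Shannon's (the only one named) | Simpson's |
| Shannon's | the listed outcome | secondary analysis |
| Simpson's | not listed | lead |
| Richness | not listed | secondary analysis |
| Timing | 1 and 3 months; change from 0 to 1 month | pre- and post-treatment; no visit in the sentence that names the indices |

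No figure in the documents depends on the index, so there is no stated number to reproduce. The sample size in Section IX is for OSDI only.

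**2. Can the indices disagree?** Take two invented communities, with Shannon = −Σ p ln p and Simpson = 1 − Σ p².

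- A, one taxon at 50% and 50 taxa at 1%: Shannon = 0.5 × 0.693 + 50 × 0.01 × 4.605 = 2.65; Simpson = 1 − (0.25 + 50 × 0.0001) = 0.745.
- B, six equal taxa: Shannon = ln 6 = 1.79; Simpson = 1 − 6 × (1/36) = 0.833.

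Shannon's ranks A as more diverse and Simpson's ranks B. This shows that a reversal is possible, not that it is likely here.

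**3. Type I error at one visit if either index may lead.** The test is two-sided at 0.05. The between-index correlation r is an assumption. With (Z₁, Z₂) bivariate normal, the error is P(max|Z| > 1.96).

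| Assumed r | Either index significant |
|---|---|
| 0.9 | 7.0% |
| 0.8 | 7.8% |
| 0.7 | 8.3% |
| 0.5 | 9.1% |

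The ceiling is 10%; independent indices would give 1 − 0.95² = 9.75%. Simulated two-sample t tests at 16 or 19 per arm (the evaluable and recruited numbers in Section IX) give 7.1% at r = 0.9 and 9.1% at r = 0.5.

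**4. How often would the two verdicts differ?** Simulated at 16 per arm, with the same standardised effect on both indices, the chance that exactly one is significant for r = 0.9 to 0.5 is:

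- no effect: 4.2% to 8.2%;
- 50% power on each: 14.9% to 34.1%;
- 80% power on each: 10.2% to 22.8%.

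Because the true effect is set equal on both indices, these figures show sampling noise between two correlated tests. They do not measure the dominant-taxa mechanism.

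**5. After one index is named.** The error is 5% at each visit. If 1 and 3 months are both tested at 0.05 and either may be claimed, the formula in step 3 gives 8.3%, 9.1% or 9.5% for assumed between-visit correlations of 0.7, 0.5 or 0.3.

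**6. Adjusting for the enrolment value.** With ρ the assumed enrolment-to-follow-up correlation, the variance relative to comparing follow-up values alone is 1 − ρ² for the adjusted model and 2(1 − ρ) for the change score.

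| Assumed ρ | Adjusted | Change score |
|---|---|---|
| 0.3 | 0.91 | 1.40 |
| 0.5 | 0.75 | 1.00 |
| 0.7 | 0.51 | 0.60 |

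At 16 per arm, the extra parameter moves the critical t from 2.042 (30 degrees of freedom) to 2.045 (29). Subtracting the enrolment value from the outcome changes only the coefficient of that covariate, so the adjusted arm difference at 1 month and its standard error are the same for the value and for the change.

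**The case against.** The strongest defence is that the sections do not flatly clash. The Simpson's sentence is introduced as an addition and poses its own question, and Shannon's is secondary in both sections. This softens the conflict but does not remove it. The construct and the arms are the same, Section VIII still ranks Shannon's below an index that Section VII never lists, and the sentence that might have linked the two names no index.

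It is also fair to say that every correlation above is assumed, and that a rise from 5% to 7–9% on one of eight secondary outcomes, for which no multiplicity control is stated, is modest. Both points stand and limit the weight of the finding.

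Baseline adjustment is not needed to cure the defect, since wording alone does that. It also keeps only the sidedness of the planned t test. It is therefore offered as a separate improvement.

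A reader might infer from Section VIII that Simpson's index competes with OSDI as the trial's primary outcome. It does not: the label there ranks indices within the alpha-diversity assessment, and Section VII sets change in OSDI at 1 month as primary.

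A reader might also infer that microbiome sampling is unplanned, because neither the Section XIII table nor the ordered list in Section XV contains it. The documents do not support that. The Section XIII table also omits the HD Analyzer measurement that Section XV requires at all three time points, so it is not exhaustive. The Manual of Procedures, which is not available here, may cover collection. The omission is a note about detail and nothing more.

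**Conclusion.** The inconsistency is on the page and should be corrected: the lead alpha-diversity index is not uniquely prespecified. That conclusion rests on the text alone and needs no assumption. Its size does need one. At a single visit, a free choice between the two indices would put the type I error at about 7.0% to 9.1%, if their correlation lies between 0.9 and 0.5. The reach is limited to the alpha-diversity secondary outcomes.

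It would be tempting to say that naming one index brings the error back to 5% outright. That holds only visit by visit; Section VII keeps both 1 and 3 months, and the plan gives no rule between them.

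**What to change.** **Main change, before unmasking.** Name one lead index, at the sponsor's choice, in identical words in Sections VII and VIII, and label the others supportive. In the same edit, state which visit leads, or state that 1 and 3 months are each reported without multiplicity control. The cost is a few lines of wording. No new data are needed.

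**Secondary improvement.** Compare the arms at 1 and 3 months in a two-sided model adjusted for the enrolment value of the lead index, in place of the plain t test. One test then answers item 2 and the 1-month part of item 1. The cost is one degree of freedom and a stated rule for participants without a usable enrolment sample. If the sponsor prefers the t test, the main change still resolves the conflict. The within-arm comparison in Section VIII can remain, using the same lead index.

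**Note.** If the Manual of Procedures sets out sample collection, a cross-reference from Sections XIII and XV would be enough. If it does not, add the sample at enrolment, 1 and 3 months, with one fixed place in the Section XV order chosen by the sponsor.
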